6.2.2. Management of Infectious Complications

Viral, bacterial, or fungal infection complications may be managed per institutional standard of care. Itacitinib may be interrupted for treatment of infectious complications at the investigator's discretion after consultation with the sponsor's medical monitor. Required modifications to the itacitinib dose in the setting of concomitant administration of certain strong CYP3A inhibitors are discussed in Section 6.1.

6.3. Concomitant Medications and Procedures

6.3.1. Permitted Medications

Concomitant treatments and/or procedures that are required to manage a participant's medical condition (including prophylactic and immunosuppressive medications as described in Section 6.3.1.1) during the study will be recorded in the eCRF.

6.3.1.1. Prophylactic Medications and Immunosuppression

Standard infection prophylaxis and immunosuppressive medications initiated before enrollment may be continued and titrated per institutional guidelines. Prophylaxis for CMV

reactivation/reinfection is not required but is strongly encouraged. Monitoring for CMV viremia is required from baseline through the EOT visit (see [Table 3](#) and Section [8.3.5](#)).

6.3.1.2. Guidelines for Concomitant Use of Antifungal Agents

If antifungal agents are adjusted such that a participant is switched from no azole to a strong CYP3A-inhibiting azole (eg, voriconazole, itraconazole, ketoconazole) during itacitinib dose administration, the itacitinib dose should be adjusted according to the guidance in Section [6.1](#). Conversely, if a participant switches from taking a CYP3A-inhibiting azole to no azole, the itacitinib dose should be adjusted according to Section [6.1](#) and [Table 9](#).

Note: [Appendix C](#) includes a list of azoles that are considered clinically relevant CYP3A inhibitors. Voriconazole, itraconazole, posaconazole, and ketoconazole are considered clinically relevant. Isavuconazole and fluconazole are not considered clinically relevant CYP3A inhibitors (these are moderate, not strong inhibitors) and do not require dose adjustment of itacitinib. Participants who are taking isavuconazole or fluconazole should be administered the dose in Column A of [Table 9](#) for a given dose level, in the absence of coadministration of any other strong CYP3A inhibitors.

6.3.2. Restricted Medications

The following medications have restrictions on use during the treatment period of the study:

- Aspirin in doses exceeding 125 mg per day is not permitted. Low-dose aspirin (≤ 125 mg per day) is permitted unless clinically contraindicated.
- If concomitant administration of an anticoagulant/antiplatelet medication is indicated, then caution and enhanced monitoring is required. History of thrombocytopenia should be a factor in the choice of anticoagulant and dose.

6.3.3. Prohibited Medications

None of the prohibited medications listed below may be initiated during study treatment. Medications initiated before the start of treatment are allowed if the specified criteria are met.

- Azithromycin must have initiated treatment ≥ 3 months before screening and must be on a stable dose.
- Montelukast must have initiated treatment ≥ 3 months before screening and must be on a stable dose.
- The following may not have been administered within the specified time frame before the start of itacitinib treatment:
 - Alemtuzumab within 6 months
 - Rabbit ATG, equine ATG, or other ATG within 3 months
 - B-cell targeting agents (eg, rituximab, proteasome inhibitors) within 3 months
 - Investigational agents within 30 days (or 5 half-lives of the investigational product, whichever is longer)
 - Nintedanib or pirfenidone within 30 days

- Concomitant use of a JAK inhibitor.
- Initiating therapy with an investigational medication unless otherwise approved by the medical monitor.
- Coadministration with strong CYP3A inducers. The [FDA website](#) provides the most current list of strong CYP3A4 inducers.
- Strong CYP3A inhibitors must have initiated treatment > 4 weeks before the first dose of study drug.

6.3.4. Prohibited Procedures

- Extracorporeal photopheresis within 6 weeks before the start of treatment.

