- **Extracorporeal Photopheresis:** ECP has demonstrated modest activity in a number of single institution studies, the largest of which enrolled 51 patients. In this study, 61% of patients had prolonged stable disease defined by FEV₁ of -5 to +5 of pre-ECP baseline maintained over 6 months ([Benden et al 2008](#)).

- Montelukast: A randomized controlled trial enrolled 30 patients to receive montelukast vs placebo. Montelukast had no effect on lung function decline in the overall cohort. However, in a post-hoc subanalysis of BOS Grade 1 patients, montelukast attenuated further decline of FEV₁ during the study period in both absolute and predicted FEV₁ ([Rutten et al 2018](#)).
- Retransplantation: The definitive therapy for progressive BOS for those who are eligible is lung retransplantation. Survival following a second transplant is markedly lower than primary transplants at 2.6 years ([Thomas et al 2015](#)).

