5.1. Inclusion Criteria

Participants are eligible to be included in the study only if all of the following criteria apply:

1. Male or female, 18 years of age or older.
2. Ability to comprehend and willingness to sign a written informed consent and assent (when appropriate) according to institutional standards and willingness to comply with all study visits and procedures.
3. Double lung transplantation \geq 1 year before informed consent.
4. Documented post-transplant baseline FEV₁ (average of the 2 highest values measured \geq 3 weeks apart per ISHLT criteria [[Meyer et al 2014](#)]) following functional recovery and stabilization post-lung transplantation.
5. Confirmed BOS progression to Grade 1, 2, or 3 (per ISHLT 2002 criteria [[Estenne et al 2002](#)]) diagnosed within 1 year of screening.
 - a. Grade 1 BOS is defined as a fractional decrease in FEV₁ to 66-80% of post-transplant baseline FEV₁.
 - b. Grade 2 BOS is defined as a fractional decrease in FEV₁ to 51-65% of post-transplant baseline FEV₁.
 - c. Grade 3 BOS is defined as a fractional decrease in FEV₁ to \leq 50% of post-transplant baseline FEV₁.

OR

Confirmed BOS Grade 1, 2, or 3 diagnosed within 2 years of screening (based on the above definitions) AND:

- a. A \geq 200 mL decrease in FEV₁ in the previous 12 months OR
- b. A \geq 50 mL decrease in FEV₁ in the last 2 measurements.

Note: BOS grade must be determined by the average of 2 measurements made \geq 3 weeks apart.

6. Participants may be taking azithromycin and/or montelukast for BOS, however, treatment must have been initiated \geq 3 months before screening and must be at a stable dose.
7. If a participant is being treated with systemic corticosteroids for BOS, then the dose must be stable for \geq 4 weeks before screening.

Note: Participants who have recently undergone a steroid taper and who are currently taking physiologic doses (\leq 10 mg/day prednisone equivalent) are not required to have been on a stable dose for \geq 4 weeks before screening.

8. Willingness to avoid pregnancy or fathering children based on the criteria below.

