5.2. Exclusion Criteria

Participants are excluded from the study if any of the following criteria apply:

1. History of a single lung transplant.
2. FEV₁ decline attributable to cause(s) other than BOS, including but not limited to clear evidence of RAS, inflammatory complications of the lung allograft, antibody mediated rejection, infection, airway dysfunction, allograft compression, impaired graft inflation, vascular obstruction, weight gain, or organizing pneumonia.
3. For participants with Grade 3 BOS as defined in inclusion criterion #5, FEV₁ at screening $< 35\%$ of post-transplant baseline.
4. Receipt of any other systemic treatment specifically for BOS (with the exception of azithromycin and montelukast), including extracorporeal photopheresis, alemtuzumab, and/or ATG within the timeframes outlined in Section [6.3.3](#) and Section [6.3.4](#) (as applicable).
5. Epstein-Barr virus-negative participants (at the time of transplant) who received donor EBV IgG positive lungs.
6. Participants who have received lungs from HCV-infected donors.
7. Removed during Protocol Amendment 2.
8. Participants who have had any significant change (eg, addition of new agents) in an immunosuppressive regimen in the 4 weeks before screening.

Note: Adjustments to dosage of maintenance immunosuppression (eg, tacrolimus) to maintain therapeutic levels are encouraged. Monitoring of CNI levels and any other agents that are used for maintenance immunosuppression (eg, mTORi) for which therapeutic drug monitoring is routinely performed as local standard of care is required at all study visits through Week 8.

9. Participant is hospitalized as an inpatient at the time of consent or at study Day 1.
Note: Participants who are not hospitalized at the time of informed consent but are later hospitalized during the screening period may be enrolled as long as all other eligibility criteria continue to be met.
10. Untreated and/or symptomatic GERD.
11. Significant infectious comorbidities including invasive fungal disease, B. Cepacia, non-TB mycobacteria, or TB.
12. History of diffuse alveolar hemorrhage.
13. Receipt of JAK inhibitor therapy after lung transplant for any indication. Treatment with a JAK inhibitor before lung transplant is permitted.
14. Participants with laboratory values at screening defined in [Table 7](#).

Table 7: Exclusionary Laboratory Values

Laboratory Parameter	Exclusion Criterion
a	ANC < $1.5 \times 10^9/L$
b	Platelet count < $120 \times 10^9/L$

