### 6.1. Demographics, Baseline Characteristics, and Medical History

Demographics, baseline characteristics, medical history, lung transplant history, BOS history, prior and concomitant medications for immunosuppression, and prior and concomitant medications for treatment of BOS will be summarized for the FAS and listed. Procedures and nondrug therapies will be listed for the FAS.

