### 7.4.2. Time to Progression or Death

Time to progression or death, defined as the interval between the start of itacitinib treatment and BOS progression (defined as a  $\geq$  10% absolute decrease in FEV1 from pretreatment baseline observed in at least 2 consecutive spirometric assessments at least 3 weeks apart) or death. The time of BOS progression follows the same definition as in Section 7.4.1. Participants with no observed BOS progression or death at the time of database lock or discontinuation will be censored at the time of last valid FEV1 assessment.

Time to progression or death will be estimated by the Kaplan-Meier method. Median duration and 95% CIs will be estimated.

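### The SAP has no rule for FEV1 measured after photopheresis or intensified BOS immunosuppression begins on treatment, so the Phase 1 response and progression tables can credit itacitinib with another therapy's effect

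*Protocol*

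**What the plan says.** **Therapy during treatment.** Photopheresis appears in Protocol 6.3.4 only as a washout: "Extracorporeal photopheresis within 6 weeks before the start of treatment". Exclusion 4 (Protocol 5.2) bars other systemic BOS treatment, "including extracorporeal photopheresis, alemtuzumab, and/or ATG within the timeframes outlined in Section" 6.3.3 and 6.3.4, which are the same pre-treatment windows. Protocol 6.3.3 opens with "None of the prohibited medications listed below may be initiated during study treatment". Its list covers azithromycin, montelukast, alemtuzumab, ATG, B-cell agents, nintedanib and pirfenidone, among others. It includes neither systemic corticosteroids nor photopheresis.

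For steroids there is an entry rule (Protocol 5.1, criterion 7): "If a participant is being treated with systemic corticosteroids for BOS, then the dose must be stable for" at least 4 weeks before screening, with an exception after a recent taper to a physiologic dose. After entry, Protocol 6.3.1.1 says: "Standard infection prophylaxis and immunosuppressive medications initiated before enrollment may be continued and titrated per institutional guidelines". Protocol 6.3.1 has concomitant treatments and procedures recorded in the eCRF.

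**Analysis.** SAP 7.3 defines response as a confirmed absolute FEV1 increase of at least 10%. Nonresponse is imputed only for study withdrawal before Week 12 or absence of FEV1 data. SAP 7.4.1 ends a response at progression, death or loss of clinical benefit, the last dated by stopping itacitinib for lack of efficacy. SAP 7.4.2 says: "Participants with no observed BOS progression or death at the time of database lock or discontinuation will be censored", at the last valid FEV1; it does not define valid.

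**Outputs.** SAP 6.1 states: "Procedures and nondrug therapies will be listed for the FAS". Appendix A contains no such listing.

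**The concern.** Protocol 6.5 rests the evidence on comparison with each participant's own pretreatment state. If a participant who stays on itacitinib also starts photopheresis, or has immunosuppression intensified for BOS, the later FEV1 course reflects both treatments and the design cannot separate them. The sponsor recognised this for prior use: the Amendment 1 rationale in Protocol Appendix E justifies the 6-week washout on the ground that the effect of photopheresis will by then be too small to confound the assessment of itacitinib. Concurrent use is the stronger case.

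At stake are the FEV1 response, FEV1 by visit, duration of response and time-to-progression tables. SAP Amendment 1 keeps all four after the decision to stop at Phase 1. SAP 8.2 also uses responder status in the pharmacodynamic models.

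**Working it through.** The plan gives no figure on this point to reproduce. The check traces the text first and then shows what one participant is worth.

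**Step 1. What applies to each therapy, and where it would be seen**

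| Therapy begun or increased on treatment | Protocol text | Planned output |
|---|---|---|
| Azithromycin, montelukast, alemtuzumab, ATG, B-cell agents, nintedanib, pirfenidone | Starting barred (6.3.3) | Listings 2.4.4 to 2.4.6 |
| Photopheresis | Nothing; 6.3.4 covers only the 6 weeks before treatment | None evident; Listing 2.4.3 is BOS history, which Protocol 8.1.6 collects at screening |
| Steroid or other immunosuppressant begun before enrollment, dose raised | Titration per institution, no direction or ceiling (6.3.1.1) | Listings 2.4.4 to 2.4.6, not linked to FEV1 |
| Systemic steroid newly started | Not listed in 6.3.3, not addressed in 6.3.1.1 | Same listings, not linked to FEV1 |

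SAP 6.1 covers prior and concomitant BOS and immunosuppressive drugs, although SAP 6.1.6 describes a summary of prior BOS medications only. Drug changes are therefore traceable. On-treatment photopheresis is the one therapy without a planned output.

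**Step 2. Apply the SAP to a participant who stays on itacitinib and receives one of the last three**

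- Response (7.3): a confirmed rise after the added therapy meets the definition, and neither ground for imputed nonresponse applies.
- Duration (7.4.1): onset is dated from that rise. The added therapy ends nothing, because loss of benefit requires stopping itacitinib.
- Time to progression (7.4.2): if the added therapy holds FEV1 above the threshold, there is no event, and follow-up runs to a last FEV1 that may itself come after the added therapy.

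**Step 3. What one participant is worth**

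Input: 8 planned per dose level (Protocol 10.1.1). One responder is 1/8 = 12.5 points. With the exact intervals named in SAP 7.3:

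- 2/8 = 25.0% (95% CI 3.2% to 65.1%)
- 1/8 = 12.5% (0.3% to 52.7%)
- 0/8 = 0% (0% to 36.9%)

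**Step 4. Illustration under an assumed rate**

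Suppose that itacitinib has no effect and that a share q of participants has a confirmed rise caused by other therapy. The chance that a group of 8 shows at least one responder is 1 − (1 − q)^8:

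- q = 2%: 15%
- q = 5%: 34%
- q = 10%: 57%
- q = 20%: 83%

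The documents support no particular q, and it may be near zero.

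**The case against.** The case against has several parts, and much of it stands.

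- **Safeguards exist.** Protocol 6.3.3 bars starting most of the named alternatives. That includes azithromycin, the only therapy for which Protocol 2.1.1 reports FEV1 rises of at least 10% (about 35% to 40% of patients). Protocol 7.1.1 requires itacitinib to stop for investigator-judged loss of benefit. These narrow the gap. They do not close it: the second depends on judgment, and loss of benefit is not an event in SAP 7.4.2.
- **Using all observed FEV1 is a recognised treatment-policy strategy.** True, and the SAP nowhere says that FEV1 after added therapy is itacitinib effect. But it does not state that strategy either, and without a control group the result describes itacitinib plus whatever was added.
- **The tables are descriptive.** Also true. No hypothesis is tested and no formal comparison between doses is made.

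Four stronger inferences are tempting, and the documents do not support them:

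- A reader might take the cited photopheresis result, "61% of patients had prolonged stable disease", to mean that such patients cannot progress here. That stability was measured against the pre-photopheresis value; progression here is measured from the pre-itacitinib baseline. In the same units, a participant already 8 below study baseline who loses 5 more is 13 below, past the threshold of 10. Nor does stability show false responses. The 61% is not a measure of size for this point.
- A reader might conclude that dose selection or the one-responder condition for Phase 2 is compromised. The sponsor decided not to proceed to Phase 2 (Protocol 2.3), so neither is live.
- A reader might infer that added therapy was used, or used unevenly by site or dose. The documents report no such use.
- A reader might say that photopheresis is permitted on treatment. It sits under a heading of prohibited procedures; the text is silent, not permissive.

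**Conclusion.** The concern holds in a narrow form. Followed as written, the SAP counts FEV1 obtained after on-treatment photopheresis, or after immunosuppression started or intensified for BOS, exactly as it counts FEV1 on itacitinib alone. A rise after such therapy would inflate response, and stability after it would lengthen time to progression. The number of participants affected is unknown. The firm figure is arithmetic: 12.5 points per reclassified responder in a planned group of 8. This assumes that at least one participant received such therapy and that FEV1 changed because of it, neither of which the documents establish. The reach is limited to descriptive Phase 1 tables. The change is still worth making, because these tables carry the trial's efficacy evidence.

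**What to change.** 1. **SAP 7.3 and 7.4.1.** State that FEV1 values after the start of photopheresis, retransplantation, or new or intensified immunosuppression given for BOS may not establish or confirm a response. A participant with no confirmed response by then is a nonresponder. Exclude from the trigger short steroid courses for other reasons and level-guided dose adjustments, which the note to exclusion criterion 8 encourages. Show the all-data result beside it.
2. **SAP 7.4.1 and 7.4.2.** Add one sensitivity Kaplan-Meier analysis that counts the start of such therapy as an event. Keep the planned analysis as the main one, since starting therapy is not the same as measured progression.
3. **SAP Appendix A.** Add the procedures listing promised in SAP 6.1, and flag on-treatment BOS therapy with start dates in Listings 2.4.4 to 2.4.6.
4. **Labelling.** Mark items 1 and 2 as post hoc if results are already known. Protocol 2.3 reports an analysis of Phase 1 data in September 2021, so this is likely to apply.
5. **Protocol 6.3.1, 6.3.1.1, 6.3.3 and 6.3.4.** Reconcile these on what applies during treatment. What is clinically permitted is the sponsor's decision. With enrollment closed, this matters only for participants still on itacitinib.

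The cost is SAP wording, one sensitivity analysis and one listing, from data the eCRF already collects. It also requires a judgment, participant by participant, on whether a change in immunosuppression was made for BOS. The reported response rate may fall slightly.

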6.4. Preparation, Handling, and Accountability

The investigator or designee must confirm appropriate temperature conditions have been maintained during transit for all study treatments received and any discrepancies are reported and resolved before use of the study treatment.

Only participants enrolled in the study may receive study treatment, and only authorized site staff may supply or administer study treatment. All study treatment must be stored in a secure, environmentally controlled, and monitored (manual or automated) area in accordance with the labeled storage conditions with access limited to the investigator and authorized site staff.

The investigator (or designee) is responsible for study treatment accountability, reconciliation, and record maintenance (ie, receipt, reconciliation, and final disposition records). Inventory and accountability records must be maintained and readily available for inspection by the study monitor and are open to inspection at any time by any applicable regulatory authorities. The investigator or designee must maintain records that document:

- Delivery of study drug to the study site.
- Inventory of study drug at the site.
- Participant use of the study drug including pill counts from each supply dispensed.
- Return of study drug to the investigator or designee by participants.

The investigational product must be used only in accordance with the Protocol. The investigator will also maintain records adequately documenting that the participants were provided the specified study drug. These records should include dates, quantities, and any available batch or serial numbers or unique code numbers assigned to the investigational product and study participants.

Completed accountability records will be archived by the site. The investigator or designee will be expected to collect and retain all used, unused, and partially used containers of study drug until verified by the study monitor (unless otherwise agreed to by the sponsor). At the conclusion of the study, the investigator or designee will oversee shipment of any remaining study drug back to the sponsor or its designee for destruction according to institutional SOPs. If local procedures mandate on-site destruction of investigational supply, the site should (where local procedures allow) maintain the investigational supply until the study monitor inspects the

accountability records in order to evaluate compliance and accuracy of accountability by the investigative site. At sites where the study drug is destroyed before monitor inspection, the monitors rely on documentation of destruction per the site SOP.

Participant handling instructions can be found in [Appendix B](#). For additional information related to IP, refer to the Pharmacy Manual.

6.5. Measures to Minimize Bias: Randomization and Blinding

This is an open-label study; no comparisons will be made between participants or against historical controls. Measurements of safety and efficacy are objective measurements, and only comparisons to pretreatment conditions will be made.

6.6. Study Treatment Compliance

Compliance with study treatment will be calculated by the sponsor based on the drug accountability documented on the eCRF by the site staff and monitored by the sponsor/designee.

6.7. Treatment After the End of the Study

For participants still benefiting from itacitinib after the end of the study, provisions will be made to provide itacitinib after discussion between the sponsor and the investigator.

